9.4.5.6 Patient global impression of change scale

In 2004, Hurst and Bolton describe the PGIC scale as a more meaningful measure of health care system performance via direct feedback from the patient. The PGIC is particularly suited to capturing clinically meaningful change that makes a difference to the patient and has been used extensively in studies of musculoskeletal conditions.

This questionnaire (see [Section 17 \[Appendix N\]](#)) will be administered by individuals trained in the administration of standardized questionnaires. Score result should not be disclosed to the blinded rater.

In Part 1, PGIC will be administered on Week 8.

In Part 2, PGIC will be administered on Weeks 13, 26, 39, and 52.

9.4.5.7 Parkinson's disease questionnaire – 39 score

The PDQ-39 is a self-completion patient-reported outcome designed to address aspects of functioning and well-being over the last month for those affected by PD (see [Section 17 \[Appendix O\]](#)). This patient-reported outcome assesses how often patients experience difficulties across different quality of life dimensions:

- Mobility (10, #1-10);
- Activities of daily living (6, #11-16);
- Emotional well-being (6, #17-22);
- Stigma (4, #23-26)
- Social support (3, #27-29);
- Cognition (4, #30-33);
- Communication (3, #34-36);
- Bodily discomfort (3, #37-39).

Moreover, the PDQ-39 assesses impact of PD on specific dimensions of functioning and well-being, with a lower score reflecting a better quality of life.

In Part 1, the changes from baseline to Week 8 in PDQ-39 will be assessed, separately for Japanese and non-Japanese patients.

In Part 2, the changes from baseline to Week 52 and from baseline to Week 104, Week 156, and Week 208 in PDQ-39 scores will be assessed.

9.4.5.8 EuroQol five dimensions questionnaire

The EQ-5D is a standardized instrument for measuring generic health status. The health status measured with EQ-5D is used for estimating preference weight for that health status, then by combining the weight with time, quality-adjusted life year can be computed (see [Section 17 \[Appendix P\]](#)). The EQ-5D is made up for two components; health state description and evaluation. In the description part, health status is measured in terms of five dimensions (5D); mobility, self-care, usual activities, pain/discomfort, and anxiety/depression. Mobility dimension asks about the person's walking ability. Self-care dimension asks about the ability to wash or dress by oneself, and usual activities dimension measures performance in "work, study, housework, family or leisure activities". In pain/discomfort dimension, it asks how much pain or discomfort they have, and in anxiety/depression dimension, it asks how much anxious or depressed they are. The respondents self-rate their level of severity for each dimension using a five-level scale. In the evaluation part, the respondents evaluate their overall health status using the visual analogue scale.

In Part 1, the changes from baseline to Week 8 in EQ-5D score will be assessed, separately for Japanese and non-Japanese patients.

In Part 2, the changes from baseline to Week 52 and from baseline to Week 104, Week 156, and Week 208 in EQ-5D scores will be assessed.

9.4.5.9 Falls efficacy scale

The Falls Efficacy Scale (FES) is used to assess perception of balance and stability during activities of daily living and to assess the patient's fear of falling (see [Section 17 \[Appendix Q\]](#)). It is a 10-item questionnaire designed to assess confidence in a person's ability to perform 10 daily tasks without falling as an indicator of how one's fear of falling impacts physical performance. Each item is rated from 1 ("very confident") to 10 ("not confident at all"), and the per item ratings are added to generate a summary total score. Total scores can range from 10 (best possible) to 100 (worst possible). Thus, lower scores indicate more confidence and higher scores indicate lack of confidence and greater fear of falling. Of note, the FES appears to be a reliable and valid method for measuring fear of falling. This scale has excellent reliability, is correlated with measures of balance and gait, and predicts future falls and decline in functional capacity. Most importantly, the FES has proven sensitive to change in fears following clinical interventions.

In Part 2, the changes from baseline to Week 52 and from baseline to Week 104, Week 156, and Week 208 in FES scores will be assessed. FES will be administered at baseline, Weeks 13, 26, 39, 52, 78, 104, 130, 156, 182, and 208.

9.4.6 Parkinson's disease progression model

The data collected during the study will be used to develop a Parkinson's disease progression model in early-stage PD patients carrying a GBA mutation.

9.5 HEALTH-RELATED PRODUCTIVITY QUESTIONNAIRE

Health-related quality of life measures are currently essential for the evaluation of patients in clinical trials. Patients with PD are particularly vulnerable to deterioration of health-related quality of life resulting from significant motor disability and the burden of nonmotor symptoms. Assessment of health-related quality of life of persons with PD is thus of essential importance.

The HRPQ contains items related to productivity during paid work, but more importantly for this population, it also has questions about ability to be productive in the home at household chores (cooking, cleaning, gardening, repairs, etc) (see [Section 17 \[Appendix R\]](#)).

In Part 1, the changes from baseline to Week 8 in HRPQ scores will be assessed, separately for Japanese and non-Japanese patients.

In Part 2, the changes from baseline to Week 52 and from baseline to Week 104, Week 156, and Week 208 in HRPQ scores will be assessed.

9.6 PHARMACOGENETIC ASSESSMENT

During the screening period, 1 blood sample will be collected for investigation of GBA mutations and the LRRK2 G2019S mutation, which is required to include patients in the study (see [Section 17 Appendix A](#)).

Approximately 6 to 10 mL whole blood will be collected for pharmacogenetic analysis during the screening period. Special procedures for collection, storage, and shipping of DNA samples for investigation of GBA mutations will be described in detail in the laboratory manual provided to the study sites.

Once these analyses have been performed, all DNA material left over will be destroyed ([Section 9.6.1](#)).

9.6.1 Optional stored DNA sample (not applicable in Israel)

Once enrollment is confirmed, patients will be asked if they are willing to consent to long-term storage of DNA samples for future use. For those patients who signed the optional Pharmacogenetic Informed Consent Form, a blood sample will be collected as specified in the study flow chart ([Section 1.3.1](#)) for the purpose of additional pharmacogenetic analysis and this sample will be stored.

In Part 2, patients who initially consented, will be asked if they consent for a second blood sample. This sample will be collected at Week 52 or at any visit after Week 52.

The data from patient's genetic material may be used to understand PD disease pathogenesis, GZ/SAR402671 signaling, drug response or activity and toxicity, to determine a possible relationship between the genes and PD or diseases, to develop and/or validate a bioassay method, possibly to identify new drug targets or biomarkers, and investigate allelic variants of drug metabolizing enzymes (DMEs) and/or drug transporters. In addition, as new scientific knowledge is gained that may be related to GZ/SAR402671, patient response or association with PD, other genes may also be studied.

This blood sample will be transferred to a Sanofi site (or a subcontractor site) which could be located outside of the country where the study is conducted. Sanofi or its subcontractor will extract DNA from the sample.

This blood sample, and the DNA that is extracted from it, will be assigned a second number, a Genetic ID that is different from the Patient ID. This "double coding" is performed to separate a patient's medical information and DNA data.

The clinical study data (coded by Patient ID) will be stored in the clinical data management system (CDMS), which in a distinct database in a separate environment from the database containing the genetic data (coded by Genetic ID). The key linking Patient ID and Genetic ID will be maintained by a third party, under appropriate access control. The matching of clinical data and pharmacogenetic data, for the purpose of data analysis, will be possible only by using this key,

which will be under strict access control. All data will be reported only in coded form in order to maintain confidentiality.

The DNA will be stored for up to 15 years from the completion of the clinical study report.

If a patient, via written request, asks for destruction of his/her samples and the samples have not yet been double coded, the Sponsor will destroy the samples per applicable guidelines; however, any data already generated will not be destroyed. The Sponsor will notify the Investigator in writing that the samples have been destroyed. However, any analyses of the sample(s) that have already been performed or data generated prior to patient's request will continue to be used as part of the research in this project and will be kept by the Sponsor.

Special procedures for collection, storage, and shipping of DNA samples are summarized in [Table 4](#) and will be described in detail in the laboratory manual provided to the study sites.

Table 4 - Summary of handling procedures for stored DNA samples

Sample Type(s)	Pharmacogenetics
Blood sample volume	Up to 8.5 mL
Tube type	Tube provided by central laboratory for DNA sample storage
Anticoagulant	See laboratory manual for specific instructions
Blood handling procedures	See laboratory manual for specific instructions
Shipping conditions	See laboratory manual for specific instructions
DNA storage conditions	70°C or colder; may also be placed temporarily on dry ice (only if the sample is being shipped frozen)

Abbreviation: DNA: deoxyribonucleic acid.

9.7 FUTURE USE OF NON-GENOMIC SAMPLES

Not all of the samples collected during this study may be required for the tests planned in this clinical trial. For patients who have consented to it, the samples that are unused or left over after testing may be used for other research purposes (excluding genetic analysis) related to PD and/or to GZ/SAR402671 other than those defined in the present protocol, as per local regulations.

These other research analyses can help to better understand PD disease pathogenesis, GZ/SAR402671 signaling, drug response or activity, and toxicity, to develop and/or validate a bioassay method, and possibly to identify new drug targets or biomarkers.

These samples (excluding genetic analysis and long-term stored DNA sample) will remain labelled with the same identifiers as the one used during the study (ie, Patient ID). They will be transferred to a Sanofi site (or a subcontractor site) which can be located outside of the countries where the study is conducted and stored for up to 5 years and as per local regulations. The Sponsor has included safeguards for protecting patient confidentiality and personal data (see [Section 14.3](#) and [Section 14.5](#)).

If a patient, via written request, asks for destruction of his/her research samples, the Sponsor will destroy the samples per applicable guidelines; however, any data already generated will not be destroyed. The Sponsor will notify the Investigator in writing that the samples have been destroyed. However, any analyses of the sample(s) that have already been performed or data generated prior to patient's request will continue to be used as part of the research in this project and will be kept by the Sponsor.

10 STUDY PROCEDURES

In order to ensure proper evaluation of efficacy, the staff of each study center will include the following physicians: a primary treating neurologist, a neurologist Sub-Investigator and a minimum of 2 blinded examining neurologist/raters. The primary treating neurologist, who can serve as the PI, will have overall responsibility to lead the site study team (physicians, pharmacists, technicians, nurses, and clinical coordinators) in all aspects of the study. The primary treating neurologist/PI will also have a neurologist Sub-Investigator who can back up the PI when/if needed. The blinded examining neurologist/raters must be experienced neurologists, or qualified non-physician health professionals who meet a predetermined level of experience in evaluating GBA-PD patients including examining GBA-PD patients and scoring the various scales when permitted by local laws, health authority rules, and ethics committee requirements. This delineation assures that AEs or other health issues for any patient do not influence the neurological assessment. Both the treating neurologist and blinded examining neurologist/ rater must have a minimum of 2 years of PD clinical experience.

Treating neurologist

The treating neurologist will be responsible for evaluation of patient eligibility; supervision of IMP administration; assessing and treating of AEs; assessing, confirming, and managing any GBA-PD issues; and monitoring of safety assessments, including routine laboratory results and concomitant medications. As much as possible, the same treating neurologist, be it the PI or Sub-Investigator, must maintain that role for a given patient throughout the study.

Examining neurologist/blinded rater

Every effort should be made to maintain the same blinded raters throughout the study. In case the rater must change, new blinded raters must be trained and remain throughout the duration of the study. For a given patient, one blinded rater does not have to perform all the assessments. However, each questionnaire (MDS-UPDRS [including H&Y], PD-CRS, MoCA, SDMT [oral], TMT-A, TMT-B, and CGI) should be scored by the same blinded rater throughout the study. Of note, only MDS-UPDRS and PD-CRS require a certified blinded rater.

The examining neurologist/blinded rater will be responsible for conducting all the efficacy assessments and for determining the scores, and must be certified for MDS-UPDRS and PD-CRS rating prior to any involvement in the study. Throughout the study, the examining neurologist/rater must not be involved with any other aspect of patient care and management and must remain blinded to the patient's treatment and safety profile (AEs, concomitant medications and laboratory results). Moreover, he/she must also not read the protocol, ensuring accurate rater-blinded assessments. This person should instead refer to the schedule of assessments.

All other investigational site staff must refrain from discussing any aspects of the protocol and/or safety issues with the examining neurologist. The examining neurologist/blinded rater should maintain the role for a given patient throughout the study. The study site is responsible for appointing a backup examining neurologist/rater in the case the primary is unable to fulfill the

role and that person is responsible for conducting the remainder of the assessments for the patient throughout the remainder of the study. The role of the treating neurologist and the examining neurologist is NOT interchangeable throughout the study even for different patients.

The Clinical Coordinator may be a nurse or physician who will be responsible for coordinating and assisting all study site staff, including patient scheduling and completion and monitoring of all patients' case report forms. He/she will be responsible for coordinating IMP administration, and collect, process, and send all blood and other forms of biological samples and requests to the central laboratory. Additionally, he/she will be responsible for administering the patient-reported questionnaires, and coordinating the conduct of the baseline MRI (without contrast).

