Abbreviations: α -Syn: α -synuclein; β -HCG: beta-human chorionic gonadotropin; AE: adverse event; BDI-II: Beck Depression Inventory, second edition; CGI: Clinical Global Impression; CSF: cerebrospinal fluid; DAT: dopamine transporters; DAT scan, ioflupane I-123 injection DaTSCAN; DBS: dried blood spot; ECG: electrocardiogram; EQ-5D: EuroQol Five Dimensions questionnaire; FES: Falls Efficacy Scale; GBA: glucocerebrosidase gene; GCase: glucocerebrosidase; GL-1: glucosylceramide; H&Y: Hoehn and Yahr; HRPQ: Health-Related Productivity Questionnaire; IMP: investigational medicinal product; LP: lumbar puncture; lyso-GL 1: glucosylsphingosine; MDS-UPDRS: Movement Disorder Society-Unified Parkinson's Disease Rating Scale; MoCA: Montreal Cognitive Assessment; MRI: magnetic resonance imaging; NFL: neurofilament light chain; PD: Parkinson's disease; PD-CRS: Parkinson's Disease-Cognitive Rating Scale; PDQ-39: Parkinson's Disease Questionnaire - 39; PGIC: Patient Global Impression of Change; PK: pharmacokinetics; qd, daily; RBD: rapid eye movement sleep behavior disorder; SDMT: Symbol Digit Modalities Test; TMT-A: Trail Making test A; TMT-B: Trail Making test B; WOCBP: women of childbearing potential.

- a For patients who have previously completed Part 1, the following will NOT have to be repeated: GBA mutation and LRRK2 screening, GCase: dried blood spot, MRI, LP, and DAT scan.
- b This visit will serve as the screening for patients enrolling into Period 3.
- c Genetic screening will not need to be repeated to confirm eligibility of patients from Part 1 to enroll in Part 2. Once the results of the GBA gene sequencing (positive for a GBA mutation) and the LRRK2 genotyping (negative for the G2019S mutation) are confirmed, the remaining of the screening activities can continue.
- d Confirmed by historically documented polysomnography or by RBD screening questionnaire.
- e Once patients demonstrate eligibility based on screening criteria, MRI, LP, and DAT scan will be performed, except for the patients who completed these baseline assessments in Part 1. Baseline MRI must be done at least 7 days prior to the end of the screening period (Day -8). DAT scans will be performed only in countries where it is approved.

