1.3.3 Part 2: Study schedule of assessments (Periods 3 and 4)

Study Period	Long-Term Follow-up Period (Period 3)												8-Week Follow-up Visit (Period 4)
	W65 ^f (±7 days)	W78 ^f (±7 days)	W91 ^f (±7 days)	W104 (2 years) ^f (±7 days)	W117 ^f (±7 days)	W130 ^f (±7 days)	W143 ^f (±7 days)	W156 ^f (3 years) (±7 days)	W169 ^f (±7 days)	W182 ^f (±7 days)	W195 ^f (±7 days)	W208 ^f (4 years) (±7 days)	
Visit number	9.1 (for Japanese patients only)	10	10.1 (for Japanese patients only)	11	11.1 (for Japanese patients only)	12	12.1 (for Japanese patients only)	13	13.1 (for Japanese patients only)	14	14.1 (for Japanese patients only)	15	16
Visit at clinical site	X	X	X	X	X	X	X	X	X	X	X	X	X
Concomitant medications	X	X	X	X	X	X	X	X	X	X	X	X	X
Study treatment administration													
GZ/SAR402671	qd												
Dispense IMP		X		X		X		X		X			
Dispense/check patient diary		X		X		X		X		X		X ^b	X ^b
Biomarkers^c													
Biomarkers: serum and plasma				X				X				X	
Safety													
Physical examination				X				X				X	X

Study Period	Long-Term Follow-up Period (Period 3)												8-Week Follow-up Visit (Period 4)
	W65 ^f (±7 days)	W78 ^f (±7 days)	W91 ^f (±7 days)	W104 (2 years) ^f (±7 days)	W117 ^f (±7 days)	W130 ^f (±7 days)	W143 ^f (±7 days)	W156 ^f (3 years) (±7 days)	W169 ^f (±7 days)	W182 ^f (±7 days)	W195 ^f (±7 days)	W208 ^f (4 years) (±7 days)	
Visit number	9.1 (for Japanese patients only)	10	10.1 (for Japanese patients only)	11	11.1 (for Japanese patients only)	12	12.1 (for Japanese patients only)	13	13.1 (for Japanese patients only)	14	14.1 (for Japanese patients only)	15	16
Neurological examination		X		X		X		X		X		X	X
Vital signs, body temperature	X	X	X	X	X	X	X	X	X	X	X	X	X
Body weight				X				X				X	
Hematology				X				X				X	
Biochemistry, urinalysis				X				X				X	
Urine pregnancy test (for WOCBP)		X		X		X		X		X		X	
Ophthalmology examination ^d		X		X		X		X		X		X	X
12-lead ECG				X				X				X	
Adverse event collection	X	X	X	X	X	X	X	X	X	X	X	X	X
Assessments^e													
DAT scan				X				X				X	

Study Period	Long-Term Follow-up Period (Period 3)												8-Week Follow-up Visit (Period 4)
	Day (D) or Week (W) (allowed range)	W65 ^f (±7 days)	W78 ^f (±7 days)	W91 ^f (±7 days)	W104 (2 years) ^f (±7 days)	W117 ^f (±7 days)	W130 ^f (±7 days)	W143 ^f (±7 days)	W156 ^f (3 years) (±7 days)	W169 ^f (±7 days)	W182 ^f (±7 days)	W195 ^f (±7 days)	

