6.5 DISCUSSION OF STUDY DESIGN

Current treatment options for PD patients, with or without GBA mutations, are limited due to side effects. Despite the many therapeutic agents available for the treatment of PD, patients can still experience intolerable disability due to disease progression. Thus, there is a high unmet medical need for better treatment alternatives in PD. Participation in this placebo-controlled study, with a novel mechanism of action, would present a unique opportunity for the patients. Patients will be allowed to start on PD therapy (only an immediate release levodopa formulation is allowed) or to continue to take their medication as usual (if already taking PD medication at study start).

Of note, PD prescription medications permitted (see [Section 8.8](#)) in this trial include:

- Dopamine replacement therapies (eg; levodopa/carbidopa).
- Dopamine agonists (eg; pramipexole, ropinirole, bromocriptine).
- Monoamine oxidase B inhibitors (eg; rasagiline).
- Catechol-O-methyltransferase inhibitors (eg; entacapone, tolcapone).
- Anticholinergics (eg; artane, cogentin).

The following points were taken into consideration in the design of the study:

- **Screening:** Sequencing of the GBA gene and genotyping for a LRRK2 (G2019S) mutation to ensure patient eligibility will be conducted from a collected whole blood sample even if historical results are available.
- **Randomization (Day 1, pre-dose):** To reduce the risk of imbalance between treatment groups with respect to cognitive function and PD medication. In Part 2, randomization will be stratified based on use of levodopa/PD medication (yes/no), cognitive function (MoCA score <26 [yes/no]) and severe GBA mutation (yes/no).
- **Long-term follow-up (Part 2):** Upon completion of the 52-week treatment period, eligible patients will be followed in an LTFU period for 36 months. Patients in the placebo arm will be switched to GZ/SAR402671 treatment after completing the Week 52 study visit. During the LTFU period, study drug assignment will remain blinded and patients will continue to be assessed by a blinded rater, thus collecting important information and

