9.4 EXPLORATORY AND OTHER ENDPOINTS

9.4.1 Pharmacodynamic and exploratory fluid biomarkers

In Part 1 and Part 2, CSF samples collected by means of a LP and plasma samples will be collected at the times specified in the schedule of assessments (see [Section 1.3](#)).

Pharmacodynamic biomarkers such as GL-1 and lyso-GL-1 in plasma and CSF, and GCase activity in dried blood spot will be measured at the Sponsor's laboratory or at a subcontracted laboratory. Additional pharmacodynamic biomarkers, such as chitotriosidase, cytokines, ceramide, and sphingomyelin in plasma and serum or chitotriosidase and cytokines in CSF may also be assessed. See [Section 17 \(Appendix H\)](#) for a list of exploratory pharmacodynamic biomarkers per body fluid.

Exploratory biomarkers to be evaluated may include:

- NFL
- α -Syn
- beta amyloid (1-40, and 1-42)
- Total tau and phospho-tau (181)

Other variables may also be assessed if available data during the course of the study suggests a relationship to disease course in PD patients or to GZ/SAR402671. Markers related to PD and/or neurodegeneration and/or GZ/SAR402671 may be assessed at the Sponsor's laboratory or at a contract research organization or an academic laboratory appointed by the Sponsor.

The number of samples per patient is shown in [Table 1](#).

Table 1 - Number of samples for pharmacodynamics assessment

Type of Samples	Plasma/Serum			Cerebrospinal Fluid		
	15 patients in Part 1	12 Japanese patients	216 patients in Part 2	15 patients in Part 1	12 Japanese patients	216 patients in Part 2
Total number of sample timepoints by patient ^a	3	3	7	2	2	2
Total number of samples for study ^a	45	36	1512	30	24	432

a Approximate total number of samples.

The assay methods will be detailed in a separate laboratory manual.

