10.1.2.10 Long term follow-up period (Period 3)

Patients who complete the 52 weeks of double-blinded treatment and who continue to meet inclusion criteria [I 06](#), [I 07](#), [I 08](#), and [I 09](#) and none of the exclusion criteria (exclusion criteria [E 02](#), [E 03](#), [E 05](#), and [E 06](#) will not need to be rechecked) will be eligible to enroll to the LTFU period (Period 3) where they will continue to receive appropriate monitoring and will receive GZ/SAR402671 treatment after Visit 9. It is important to note that patients will not be informed of when the switch will occur, nor will the person(s) performing any of the evaluations.

Throughout Period 3, a visit window of ± 7 days for all visits is acceptable using Day 1 as reference.

During this period, a clinic visit will be scheduled at 6-month intervals (Weeks 78, 104, 130, 156, 182, and 208) and patients will receive GZ/SAR402671, orally, at the clinic. For Japanese patients only, additional clinic visit will be scheduled at Weeks 65, 91, 117, 143, 169, and 195 (Visits 9.1, 10.1, 11.1, 12.1, 13.1, and 14.1) in addition to the above 6-month interval visits.

Before dosing, the following assessments will be performed at each study visit (every 6 months), as listed in the study flow chart, [Section 1.3.3](#), which should be done in the following order:

- Whenever possible, the following scales and questionnaires should be done prior to clinical interaction with the Investigator:
 - BDI-II ([Appendix L](#))
 - PDQ-39 ([Appendix O](#))
 - EQ-5D ([Appendix P](#))
 - HRPQ ([Appendix R](#))
 - FES ([Appendix Q](#))
- MDS-UPDRS, including H&Y ([Appendix F](#))
- PD-CRS ([Appendix G](#))
- Other questionnaires and scales
 - MoCA ([Appendix I](#))

- Oral SDMT ([Appendix J](#))
- TMT-A; TMT-B ([Appendix K](#))
- Review of concomitant medications (every 3 months [13 weeks] for Japanese patients only)
- General neurological examination
- Visual acuity check, slit lamp examination, and fundoscopy without pupil dilation at Visits 10, 12, and 14; at Visits 11, 13, and 15, patients will have a full ophthalmology examination and photography (must be performed after the neurological examination)
- Vital signs: systolic and diastolic blood pressure (mm Hg), heart rate (bpm), respiratory rate (breaths/minute), and temperature (°C) (every 3 months [13 weeks] for Japanese patients only)
- Urine pregnancy test (for WOCBP)

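### Section 10 sends the blinded rater to a schedule of assessments that discloses the Week 52 switch to active drug, exposing exploratory within-group change in Period 3 to rater expectation

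*Protocol*

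**What the plan says.** Section 10 (Examining neurologist/blinded rater) requires the rater to stay blinded to the patient's treatment and safety profile. It bars the rater from the protocol and names what to use in its place: "Moreover, he/she must also not read the protocol, ensuring accurate rater-blinded assessments. This person should instead refer to the schedule of assessments".

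Two other places state what the rater is meant not to know:

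- Section 10.1.2.10, on the long-term follow-up (LTFU), says that "patients will not be informed of when the switch will occur, nor will the person(s) performing any of the evaluations". The Clinical Trial Summary repeats this under the duration of the study.
- Section 6.5 says: "During the LTFU period, study drug assignment will remain blinded and patients will continue to be assessed by a blinded rater".

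The protocol uses the term schedule of assessments for its own Section 1.3. That term stands in the headings of Sections 1.3.1 to 1.3.3, and Section 9.4.1 uses it with a cross-reference to Section 1.3 when it has samples taken "at the times specified in the schedule of assessments". No rater-specific or masked version is described anywhere.

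**The concern.** The protocol treats knowledge of the switch as a risk to the ratings and sets up a safeguard against it. The safeguard then points the rater to the pages that state the switch.

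The stake is the reading of long-term efficacy. Section 5.2.3 makes long-term efficacy over 156 weeks an exploratory objective. The Clinical Trial Summary lists changes from baseline to Weeks 104, 156 and 208 as exploratory endpoints, and many of these are scored by the rater. A rater who knows that patients in Period 3 are assigned active drug may score with that expectation, and no later analysis can restore the masking.

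**Working it through.** The protocol gives no figure on this point, so the check sets the passages side by side.

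**1. Which document the rater needs.** Ratings continue after Week 52. The rows for MDS-UPDRS (with H&Y), PD-CRS, MoCA, SDMT and TMT-A/TMT-B at Weeks 78, 104, 130, 156, 182 and 208 are in Section 1.3.3. A rater told to work from the schedule has to consult that table.

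**2. What the schedules show.**

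| Feature | Section 1.3.2 (to Week 52) | Section 1.3.3 (after Week 52) |
|---|---|---|
| Period label | Blinded treatment period | "Long-Term Follow-up Period (Period 3") |
| Treatment row | GZ/SAR402671 or placebo | GZ/SAR402671 once daily, no placebo |
| Week 52, footnote b | "This visit will serve as the screening for patients enrolling into Period 3" | n/a |
| Week 52, footnote g | Dispensing applies only to patients going on to Period 3 | n/a |
| Visit 16, footnote a | n/a | Falls 8 weeks after the last dose |

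The two treatment rows show that placebo ends. The Week 52 footnotes show when. Together they disclose both the existence and the timing of the switch, which is the fact Section 10.1.2.10 withholds.

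**3. What the schedules do not show.** Nothing in either table identifies the arm to which a patient was randomised.

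**4. Which comparisons are exposed.** As a working assumption, let knowledge of the switch add the same average shift *e* to ratings in Period 3 whatever the original arm, because the rater does not know that arm. Let δ be the true change after Week 52.

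- Observed change, placebo-start group: δ_P + *e*
- Observed change, active-start group: δ_A + *e*
- Difference between groups: (δ_P + *e*) − (δ_A + *e*) = δ_P − δ_A

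The shift cancels in the comparison that Section 6.5 describes, treatment from randomisation against treatment begun one year later. It does not cancel in the change within either group, or in a pooled description of long-term change. The Week 52 primary endpoint (Section 9.1.2) and secondary endpoints (Section 9.2.2) are rated before the switch, so they contain no *e*.

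**5. Which items are exposed.** Under Section 9.1, MDS-UPDRS Parts IB and II are completed by the patient. The rater scores Parts IA and III, and Part IV for patients on PD medication. Rater expectation therefore acts on those parts, H&Y, PD-CRS, MoCA, SDMT and TMT. Part II, one half of the II+III pairing, is not scored by the rater.

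**The case against.** The best defence is that Sections 1.3.2 and 1.3.3 are themselves protocol text. Handing those pages to the rater would breach the ban in the preceding sentence, so a separate visit list must have been meant. That is a sensible intention, but the text does not state it. The only thing the protocol calls a schedule of assessments is Section 1.3, and the instruction offers it as the substitute.

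An earlier entry in the amendment history calls Period 3 open-label. The current text of Sections 6.5 and 10.1.2.10 promises concealment from evaluators, and the current text governs.

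The objections to the reach of the point do stand. A reader might infer more than the documents support:

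- *That the main result is unblinded.* It is not. The arm stays hidden, and the primary and secondary endpoints precede the switch.
- *That a step from Week 52 to Week 78 in placebo-start patients cannot be separated from expectation.* This is too strong. Patients on active drug from randomisation are a concurrent comparator, rated by people who do not know who is who.
- *That everyone is on active drug after Week 52.* Only patients eligible at Week 52 enter Period 3. Section 10.3.4 asks those who stop drug to keep attending efficacy visits, and Visit 16 is off drug.
- *That the bias can be sized against the planned 4.06 points.* That figure is the between-arm planning difference at Week 52, a different quantity, and the documents give no estimate of an expectation shift.
- *That masking the importance of the Week 52 visit is lost.* The protocol never promises such masking.

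Section 11.4.2.3 also limits p-values for exploratory endpoints to descriptive use.

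**Conclusion.** The instruction in Section 10 contradicts the concealment promised in Section 10.1.2.10 and the Clinical Trial Summary, and it should be corrected. The exposure is limited to exploratory within-group change after Week 52 on rater-scored items. It covers six visits, in those patients who enter Period 3 (at most about 216 from the planned Part 2 sample; the number entering is not stated). Its size in points cannot be derived from the documents.

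The conclusion rests on two assumptions: that the rater uses Section 1.3 as directed, and that no masked version is supplied outside the protocol. The protection of the early- versus delayed-start comparison assumes that raters cannot guess the original arm, so that any expectation falls on both groups alike. That is why it is described as largely rather than fully protected.

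Visit 16 is a neighbouring case. Amendment 06 added MDS-UPDRS there to document the course after treatment stops, and footnote a tells the rater that the patient is off drug. The protocol does not promise to conceal this, so it is no contradiction, but the same remedy covers it.

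**What to change.** In Section 10, replace the direction to the schedule of assessments with a direction to a rater-specific schedule. That schedule should list visit numbers and the scales to be scored, and nothing else: no period labels, no treatment or dispensing rows, and no footnotes on Period 3 or the last dose. Add a sentence that raters are not to be given Section 1.3.2 or 1.3.3.

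The cost is one extra page for the rater file and a short text change. Two limits remain. Raters who have already seen Section 1.3.3 cannot be re-masked, so sites should record who has, and the long-term ratings can be described with that in view. A scales-only list will also still show wider visit spacing after Week 52, so a rater may suspect a change of phase, but the list will no longer state which treatment is given.
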